6.11 Definition of Maximum Tolerated Dose and Recommended Phase II Dose

The MTD will be determined if the following conditions are met:

1. At least 6 patients have been treated at this dose and associated treatment regimen (ie, fixed-dose, 1-step IPE, or 2-step IPE).
2. The dose has the highest posterior probability that the true DLT rate is in the target interval for toxicity (16%–33%), as predicted by the BLRM. The interval boundaries of 16% and 33% are chosen to be consistent with the traditional 3+3 design toxicity boundary (ie, 1/6 and 1/3).
3. The dose satisfies the EWOC principle (the probability that the DLT rate lies within the excessive toxicity or the unacceptable toxicity window is less than 25%).

The RP2D will be defined as the dose and associated treatment regimen selected for further evaluation in Phase II by the SST. The RP2D will be determined from a synthesis of all data available, including safety, tolerability, PK, pharmacodynamics, and preliminary anti-tumor activity observations from Phase I. The RP2D must not exceed the MTD as determined by the BLRM. A minimum of 6 patients will be treated at the RP2D in Phase I and monitored through the DLT evaluation period before enrollment in Phase II may begin.

During Phase II, following enrollment of at least 12 subjects, if the observed rate of Grade 3 and/or Grade 4 toxicity considered related to IMCnyeso and meeting the definition of DLT is > 30%, a safety teleconference will be convened with the SST to determine if the cohorts should continue enrollment.

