6.12 Definitions of Dose-Limiting Toxicity

A DLT is defined as an AE or abnormal laboratory value assessed as having a suspected relationship to study drug that occurs within the DLT evaluation period (Section 6.10.2), is unrelated to disease, disease progression, inter-current illness, or concomitant medications, and meets any of the criteria included in Table 6-3. Any death not clearly due to the underlying disease or extraneous causes will be considered a DLT. Other clinically significant toxicities, including a single event or multiple occurrences of the same event that lead to a dosing delay or interruption lasting > 7 days in Cycle 1, may be considered a DLT by the SST, even if not \geq Grade 3. Events meeting DLT criteria but occurring outside the DLT evaluation period may also be considered DLT by the SST. In the absence of clinically significant signs or symptoms, abnormal laboratory values that potentially meet DLT criteria must be confirmed by re-testing at least 24 hours after the initial observation.

Cytokine release syndrome will be graded based on the ASTCT 2019 criteria in [Section 13.1](#). NCI CTCAE version 4.03 will be used for all other grading. The Investigator must notify the Sponsor within 24 hours of any DLT (additional events requiring reporting within 24 hours are listed in [Section 8.5](#)).

Guidance for toxicity management is in [Section 6.15](#).

Table 6-3: Criteria for Defining Dose-Limiting Toxicities

DLTs include \geq Grade 3 AE occurring during the DLT evaluation period, with a suspected relationship to study drug, with the following modifications:	
Hematology	Grade 4 neutropenia persisting > 5 days after onset or associated with infection is a DLT \geq Grade 3 febrile neutropenia is a DLT Grade 4 thrombocytopenia or \geq Grade 3 thrombocytopenia associated with \geq Grade 3 bleeding is a DLT Grade 4 anemia is a DLT \geq Grade 3 lymphopenia in the presence of an infection indicating clinical significance is a DLT

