Hepatic and pancreatic	Grade ≥ 2 elevated total bilirubin ($> 2 \times$ ULN) with concurrent Grade ≥ 2 elevated ALT and/or AST ($> 3 \times$ ULN), with no clear alternate etiology (eg, biliary obstruction with elevated alkaline phosphatase), is a DLT Grade 3 isolated ALT and/or AST ($> 5-8 \times$ ULN) elevation or Grade 3 isolated bilirubin elevation ($> 3-5 \times$ ULN) that does not resolve to \leq Grade 1 within 14 days of onset is a DLT \geq Grade 3 isolated ALT and/or AST ($> 8 \times$ ULN) elevation or \geq Grade 3 isolated bilirubin ($> 5 \times$ ULN) elevation is a DLT \geq Grade 3 amylase and/or lipase elevation, with associated clinical signs, symptoms, or radiographic evidence of pancreatitis, is a DLT
Gastrointestinal	Grade 3 nausea, vomiting or diarrhea persisting for > 3 days after onset, despite optimal therapy, is a DLT
Hypotension	Grade 3 hypotension that does not resolve to \leq Grade 1 within 6 hours of onset, despite optimal therapy, is a DLT Grade 4 hypotension of any duration and with any management is a DLT
Hypertension	Grade 3 hypertension (systolic BP ≥ 160 mm Hg or diastolic BP ≥ 100 mm Hg) persisting > 2 days after onset, despite treatment, is a DLT Grade 4 hypertension of any duration is a DLT
Infection	Grade 3 infection or fever in the absence of neutropenia that persists > 7 days after onset is a DLT Grade 4 infection of any duration is a DLT

DLTs include \geq Grade 3 AE occurring during the DLT evaluation period, with a suspected relationship to study drug, with the following modifications:	
Tumor Flare	Grade 3 inflammatory reaction at a tumor site associated with local anti-tumor immune response that does not resolve to \leq Grade 2 within 7 days after onset is a DLT
Electrolyte Abnormalities	Grade 3 electrolyte abnormalities that do not resolve to \leq Grade 1 within 3 days after onset, despite optimal medical management, are DLTs Grade 4 electrolyte abnormality of any duration is a DLT
Skin toxicity	Grade 3 rash and/or pruritis that persists $>$ 7 days after onset, despite optimal medical management, is a DLT Grade 4 cutaneous toxicity of any duration is a DLT
Fatigue	\geq Grade 3 fatigue that persists $>$ 4 days after onset is a DLT
Infusion-related reaction / hypersensitivity / anaphylaxis	Grade 3 infusion-related reaction that does not resolve to \leq Grade 1 within 6 hours of onset, despite appropriate medical management, is a DLT Grade 4 infusion reaction is a DLT

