8.4 Assessment of Causality

The Investigator decides whether he or she interprets the observed AE as either related to disease, to the study medication, study procedure, or other concomitant treatment or pathologies. To assess the relationship of the AE to the study drug, the following terms are defined:

- **Related:** A direct cause and effect relationship between the study treatment and the AE is likely
- **Possibly related:** A cause and effect relationship between the study treatment and the AE has not been demonstrated at this time and is not probable, but is also not impossible
- **Not related:** Without question, the AE is definitely not associated with the study treatment

All "related" and "possibly related" AEs and SAEs will be defined as related to study drug.

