8.5 Adverse Event Reporting

The Investigator must notify the Sponsor within 24 hours of any SAE, DLT, \geq Grade 2 CRS, or \geq Grade 3 hepatic function abnormality.

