13.1.2 CRS Grading Criteria

Events of CRS are to be graded based on presence of fever and treatment provided for hypotension and/or hypoxia, as shown in Table 13-1. Associated constitutional symptoms and/or organ toxicities do not influence CRS grading (and are to be graded individually per CTCAE v4.03, consistent with AE grading for this study). In patients who have CRS and then receive treatment with anti-pyretics or anti-cytokine therapy (eg, tocilizumab or steroids), fever is no longer required to grade subsequent CRS severity. In patients experiencing hypotension and hypoxia, grading is to be assigned based on the more severe event.

Table 13-1: ASTCT CRS Grading Criteria

Grade	Fever	with Hypotension	and/or Hypoxia
1	≥ 38.0 °C	None	None
2	≥ 38.0 °C	Not requiring vasopressors	Requiring oxygen delivered by low-flow nasal cannula (≤ 6 L/min) or blow-by
3	≥ 38.0 °C	Requiring a vasopressor with or without vasopressin	Requiring oxygen delivered by high-flow nasal cannula (>6L/min), facemask, nonrebreather mask, or Venturi mask
4	≥ 38.0 °C	Requiring multiple vasopressors (excluding vasopressin)	Requiring oxygen delivered by positive pressure (eg, CPAP, BiPAP, intubation and mechanical ventilation)

BiPAP = bilevel positive airway pressure; CPAP = continuous positive airway pressure; min = minute.

Grade 5 CRS is defined as death due to CRS in which another cause is not the principle factor leading to this outcome.

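### The Phase II toxicity trigger in Protocol Section 6.11 leaves out a patient whose only DLT is recorded as Grade 5, or is the concurrent hepatic criterion with both components at Grade 2

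*Protocol*

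**What the plan says.** Protocol Section 6.11 gives the only numeric toxicity rule for Phase II. After at least 12 subjects are enrolled, the SST meets by teleconference to decide whether the cohorts should go on enrolling, "if the observed rate of Grade 3 and/or Grade 4 toxicity considered related to IMCnyeso and meeting the definition of DLT is > 30" percent. An event must therefore pass three tests together: Grade 3 or 4, considered related, and a DLT.

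The DLT definition reaches further:

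- **Deaths.** Section 6.12: "Any death not clearly due to the underlying disease or extraneous causes will be considered a DLT". The header of Table 6-3 covers Grade 3 and above with no upper limit, and Section 13.1.2 provides for a fatal grade of CRS: "Grade 5 CRS is defined as death due to CRS in which another cause is not the principle factor leading to this outcome".
- **Concurrent liver abnormality.** Table 6-3 makes bilirubin of Grade 2 or more (above 2 x ULN) together with ALT and/or AST of Grade 2 or more (above 3 x ULN), "with no clear alternate etiology (eg, biliary obstruction with elevated alkaline phosphatase), is a DLT". No Grade 3 component is needed.
- **SST discretion.** Some lower-grade events that delay dosing in Cycle 1 "may be considered a DLT by the SST, even if not" Grade 3. Separately, "Events meeting DLT criteria but occurring outside the DLT evaluation period may also be considered DLT by the SST".

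The SAP does not restate the trigger. Its Sections 4 and 8.1 plan tables or summaries of Phase II DLTs, and its Section 8.2.3 treats Grade 5 as a severity level of its own.

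**The concern.** The grade restriction cannot be read as shorthand for DLT, because it removes events that the protocol itself defines as DLTs. A related Grade 3 event that meets Table 6-3 counts towards the 30%. A related death recorded only as Grade 5 does not.

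Both omitted event types were put into the definition on purpose. The Amendment 1 rationale says the definition was modified to cover Grade 5 events of uncertain cause, and the Amendment 2 change table says the concurrent hepatic criterion was aligned with potential Hy's Law. No reason is given for leaving either out of the Phase II count, so oversight looks likelier than intent. That is an inference.

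At stake is a mandatory safety review that could fail to be required although more than 30% of patients had a related DLT.

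**Working it through.** The plan states no operating characteristic for this rule, so there is no figure to reproduce.

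**1. Can the omitted events occur?** By the Table 6-3 cut-offs, Grade 3 bilirubin starts above 3 x ULN and Grade 3 ALT/AST above 5 x ULN. Bilirubin above 2 and up to 3 x ULN with ALT/AST above 3 and up to 5 x ULN therefore meets the concurrent criterion with neither component at Grade 3. A fatal event can be recorded as Grade 5 alone, since SAP Section 8.2.3 presents the most extreme severity captured.

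**2. Where is the boundary?** Smallest k with k/n > 0.30, and the rate if one patient is left out:

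| n | 0.30 x n | smallest k | k/n | (k − 1)/n |
|---|---|---|---|---|
| 12 (minimum in Section 6.11) | 3.6 | 4 | 33.3% | 25.0% |
| 27 (three cohorts of 9) | 8.1 | 9 | 33.3% | 29.6% |
| 72 (three cohorts of 24) | 21.6 | 22 | 30.6% | 29.2% |

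One uncounted patient at the boundary removes the requirement for a call. Away from the boundary, one patient changes nothing.

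**3. Illustration of size.** Let p be the true DLT rate and f the share of DLT patients whose only DLT is uncounted. The counted rate is q = p(1 − f). For a single look at n = 12,

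P(call) = 1 − Σ C(12, x) q^x (1 − q)^(12 − x), summed over x = 0 to 3.

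Example: p = 0.33, f = 0.10, q = 0.297. The four terms are 0.0146 + 0.0739 + 0.1716 + 0.2417 = 0.5018, so P(call) = 0.498.

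For checks after every patient, an exact recursion gives the chance that k/n exceeds 0.30 at any n from 12 to N. Chance of a call with f = 0 / 5% / 10%:

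| True DLT rate | single look, n = 12 | checks from 12 to 27 | checks from 12 to 72 |
|---|---|---|---|
| 20% | 20.5 / 18.0 / 15.5% | 32.1 / 28.1 / 24.4% | 35.0 / 30.3 / 26.0% |
| 33% | 59.7 / 54.9 / 49.8% | 81.0 / 76.3 / 71.0% | 91.9 / 87.7 / 82.3% |
| 40% | 77.5 / 73.0 / 68.0% | 93.9 / 91.3 / 87.8% | 99.2 / 98.3 / 96.7% |

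The 33% row is the lower limit of excessive toxicity in Table 13-5; 20% lies inside the 16–33% target band. At n = 12 and p = 0.33, the assumed shares amount to 12 x 0.33 x 0.05 = 0.20 and 12 x 0.33 x 0.10 = 0.40 uncounted patients on average.

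The values of f, the checking schedule and the pooling of cohorts are all assumptions. Section 6.11 specifies neither schedule nor pooling.

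**The case against.** The strongest case is that almost nobody falls into the gap and that deaths are dealt with elsewhere.

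- **Few patients are missed.** Grade 4 CRS of any duration is already a DLT in Table 6-3, and Section 13.1.2 defines Grade 4 by multiple vasopressors or positive-pressure oxygen. Most patients who die of CRS would have had such an event first, and Section 6.11 does not say that only the final grade counts. The hepatic case needs both components in narrow bands with no other cause. This stands, and it is why the point is minor. It does not cover a death with no qualifying Grade 3 or 4 DLT before it, or one recorded only at Grade 5.
- **Deaths are escalated individually.** Section 8.5: "The Investigator must notify the Sponsor within 24 hours of any SAE, DLT". The sponsor can act on benefit-risk at any time, and nothing bars an earlier SST call. True, but these routes are discretionary or descriptive. None puts the patient in the rate that makes the call mandatory.
- **The data suggest no problem.** Section 1.4 reports 15 patients with no DLT and no fatal AE. Also, a true rate of 33% or 40% would mean an RP2D above target despite the overdose-control rule. Both are fair, and they are reasons not to lean on the probabilities.
- **The trade-off is about even.** With checks from 12 to 72, counting all DLTs adds 4.2 to 9.6 points at a true 33% and 4.7 to 9.0 points at 20%. For a single look at n = 12 the gain (4.8 to 9.9 points) exceeds the cost (2.5 to 5.0 points). Since the outcome is a teleconference and not a stop, the extra calls are tolerable.

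**Conclusion.** The point holds as a matter of wording. The trigger uses a narrower set of events than the protocol's own DLT definition, and two event types that the protocol treats as dose-limiting fall outside it. The effect is small: one patient at the boundary, and only whether a teleconference is compulsory. The discrepancy needs no assumption. The probabilities need three (share, schedule, pooling) and should be read as illustration only.

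A reader might infer more than the documents support:

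- *That a related death in Phase II could go unseen.* It could not: DLTs and SAEs reach the sponsor within 24 hours.
- *That the relatedness filter also drops deaths of uncertain cause.* Section 8.4 says that related and possibly related "AEs and SAEs will be defined as related to study drug", and reserves unrelated for events that are definitely not associated with treatment.
- *That a stopping rule is broken.* The rule convenes a discussion; it does not stop enrollment.
- *That the trial loses a known amount of protection.* No document gives the share of DLT patients who would go uncounted.
- *That every DLT should count.* Leaving discretionary DLTs below Grade 3 out of a mandatory count is a defensible choice.

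This is a minor safety-rule correction for the next amendment.

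**What to change.** Replace the condition in Section 6.11 and leave the 12-subject minimum, the 30% threshold and the teleconference as they are. Proposed condition:

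> the observed proportion of patients who have had at least one toxicity judged related or possibly related to IMCnyeso that satisfies the Section 6.12 DLT definition, and that is either of Grade 3, 4 or 5 or an instance of the Table 6-3 concurrent hepatic criterion, exceeds 30%

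The hepatic branch must stay tied to the Section 6.12 definition. If it stood alone, late or unconfirmed Grade 2 elevations would count, because the 28-day window, the attribution exclusions and the confirmatory re-test at least 24 hours later would no longer apply to it. Out-of-window Grade 3 and 4 events are handled as they are now, and discretionary DLTs below Grade 3 stay out.

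The cost is one sentence and somewhat more calls when toxicity is acceptable. For a single look at n = 12 and a true 20% rate, the chance of a call is 20.5% instead of 15.5–18.0% under the assumed 5–10% share. With repeated checks it is 32.1% instead of 24.4–28.1% (12 to 27) and 35.0% instead of 26.0–30.3% (12 to 72).

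The change is not a rule for single deaths. One related death plus two other DLT patients in 12 is still 3/12 (25.0%), with no mandatory call.

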6.12 Definitions of Dose-Limiting Toxicity

A DLT is defined as an AE or abnormal laboratory value assessed as having a suspected relationship to study drug that occurs within the DLT evaluation period (Section 6.10.2), is unrelated to disease, disease progression, inter-current illness, or concomitant medications, and meets any of the criteria included in Table 6-3. Any death not clearly due to the underlying disease or extraneous causes will be considered a DLT. Other clinically significant toxicities, including a single event or multiple occurrences of the same event that lead to a dosing delay or interruption lasting > 7 days in Cycle 1, may be considered a DLT by the SST, even if not \geq Grade 3. Events meeting DLT criteria but occurring outside the DLT evaluation period may also be considered DLT by the SST. In the absence of clinically significant signs or symptoms, abnormal laboratory values that potentially meet DLT criteria must be confirmed by re-testing at least 24 hours after the initial observation.

Cytokine release syndrome will be graded based on the ASTCT 2019 criteria in [Section 13.1](#). NCI CTCAE version 4.03 will be used for all other grading. The Investigator must notify the Sponsor within 24 hours of any DLT (additional events requiring reporting within 24 hours are listed in [Section 8.5](#)).

Guidance for toxicity management is in [Section 6.15](#).

Table 6-3: Criteria for Defining Dose-Limiting Toxicities

DLTs include \geq Grade 3 AE occurring during the DLT evaluation period, with a suspected relationship to study drug, with the following modifications:	
Hematology	Grade 4 neutropenia persisting > 5 days after onset or associated with infection is a DLT \geq Grade 3 febrile neutropenia is a DLT Grade 4 thrombocytopenia or \geq Grade 3 thrombocytopenia associated with \geq Grade 3 bleeding is a DLT Grade 4 anemia is a DLT \geq Grade 3 lymphopenia in the presence of an infection indicating clinical significance is a DLT
Hepatic and pancreatic	Grade ≥ 2 elevated total bilirubin ($> 2 \times$ ULN) with concurrent Grade ≥ 2 elevated ALT and/or AST ($> 3 \times$ ULN), with no clear alternate etiology (eg, biliary obstruction with elevated alkaline phosphatase), is a DLT Grade 3 isolated ALT and/or AST ($> 5-8 \times$ ULN) elevation or Grade 3 isolated bilirubin elevation ($> 3-5 \times$ ULN) that does not resolve to \leq Grade 1 within 14 days of onset is a DLT \geq Grade 3 isolated ALT and/or AST ($> 8 \times$ ULN) elevation or \geq Grade 3 isolated bilirubin ($> 5 \times$ ULN) elevation is a DLT \geq Grade 3 amylase and/or lipase elevation, with associated clinical signs, symptoms, or radiographic evidence of pancreatitis, is a DLT
Gastrointestinal	Grade 3 nausea, vomiting or diarrhea persisting for > 3 days after onset, despite optimal therapy, is a DLT
Hypotension	Grade 3 hypotension that does not resolve to \leq Grade 1 within 6 hours of onset, despite optimal therapy, is a DLT Grade 4 hypotension of any duration and with any management is a DLT
Hypertension	Grade 3 hypertension (systolic BP ≥ 160 mm Hg or diastolic BP ≥ 100 mm Hg) persisting > 2 days after onset, despite treatment, is a DLT Grade 4 hypertension of any duration is a DLT
Infection	Grade 3 infection or fever in the absence of neutropenia that persists > 7 days after onset is a DLT Grade 4 infection of any duration is a DLT

DLTs include \geq Grade 3 AE occurring during the DLT evaluation period, with a suspected relationship to study drug, with the following modifications:	
Tumor Flare	Grade 3 inflammatory reaction at a tumor site associated with local anti-tumor immune response that does not resolve to \leq Grade 2 within 7 days after onset is a DLT
Electrolyte Abnormalities	Grade 3 electrolyte abnormalities that do not resolve to \leq Grade 1 within 3 days after onset, despite optimal medical management, are DLTs Grade 4 electrolyte abnormality of any duration is a DLT
Skin toxicity	Grade 3 rash and/or pruritis that persists $>$ 7 days after onset, despite optimal medical management, is a DLT Grade 4 cutaneous toxicity of any duration is a DLT
Fatigue	\geq Grade 3 fatigue that persists $>$ 4 days after onset is a DLT
Infusion-related reaction / hypersensitivity / anaphylaxis	Grade 3 infusion-related reaction that does not resolve to \leq Grade 1 within 6 hours of onset, despite appropriate medical management, is a DLT Grade 4 infusion reaction is a DLT
Cytokine release syndrome	Grade 3 cytokine release syndrome that does not resolve to \leq Grade 2 within 6 hours after onset, despite optimal medical management (eg, corticosteroid dosing), is a DLT Grade 4 cytokine release syndrome of any duration is a DLT

ALT = alanine aminotransferase; AST = aspartate aminotransferase; DLT = dose-limiting toxicity; SST = Study Safety Team; ULN = upper limit of normal.

